5.3.2. Clinical Laboratory Parameters

Hematology, chemistry, lipid panel, and urinalysis results will be summarized and listed. Pregnancy test will not be summarized but will be listed. Summaries will include descriptive statistics for actual values and change from baseline. Shift tables from baseline condition to the condition at each visit will also be provided. The shift table will include subjects without data so that all subjects in the safety population at the baseline of each period (RI, RW, and LTE) will be included.

A summary of hepatic function abnormalities will be provided for the following criteria:

- >2xULN
- >3xULN
- >5xULN
- The number of percentage of subject's meeting the criteria for Hy's Law defined as elevations in ALT and/or AST of $\geq 3xULN$ with accompanying elevations in total bilirubin of $\geq 2xULN$ will also be summarized.

The incidence rate per 100 subject-years and its 95% CI for the following lab abnormalities will be calculated:

- Incidence of ALT >5xULN,

- Incidence of AST >5x ULN,
- Incidence of total bilirubin >2xULN
- Incidence of absolute neutrophil count (ANC) <1.0 x 10³ uL.

Multiple lab abnormalities within a subject will be counted as multiple events within the follow-up period defined in Section 5.3.1 .

Incidence rate per 100 subject years in a cohort = $100 \times (\# \text{ of different lab abnormalities from all subjects within the follow-up period}) / (\text{Sum of follow-up duration in years from all subjects in the cohort})$.

5.3.2.1. Hematology

Hematology tests performed at central study laboratory include WBC count with differential, platelet count, red blood cell count, mean corpuscular volume, hemoglobin, mean corpuscular hemoglobin concentration.

5.3.2.2. Chemistry

Blood chemistry tests performed in the central study laboratory include albumin, total protein, alkaline phosphatase, alanine aminotransferase/serum glutamic pyruvic transaminase (ALT/SGPT), aspartate aminotransferase/serum glutamic oxaloacetic transaminase (AST/SGOT), direct bilirubin, total bilirubin, bicarbonate, chloride, potassium, sodium, creatinine, glucose.

5.3.2.3. Non-fasting Lipid Panel

Subjects treated with riloncept may experience increases in their lipids, including total cholesterol, low-density lipoprotein (LDL), high-density lipoprotein HDL, and triglycerides.

Non fasting measurements of total cholesterol, triglycerides, HDL, and direct LDL will be performed by central study laboratory as described in the Schedule of Assessments in Section 13.1.

Investigators should monitor the lipid profiles in study subjects and consider ordering fasting lipid panel and/or lipid lowering therapies as needed based on cardiovascular risk factors and current guidelines.

5.3.2.4. Urinalysis

Urinalysis performed by the central study laboratory includes specific gravity, pH, protein, urobilinogen, ketones, glucose, blood, bilirubin, nitrites, leukocyte esterase will be summarized.

5.3.2.5. Pregnancy Test

For women of child-bearing potential, a urine pregnancy test using a licensed test (dipstick) should be performed prior to receiving the first administration of study drug, and as needed during the study, and also at the SFU visit. When needed, serum pregnancy test should be performed. Pregnancy test results will not be summarized but will be listed.

5.3.3. Vital Signs

Descriptive summaries of actual values and changes from baseline will be calculated for Temperature, Systolic Blood Pressure (SBP), Diastolic Blood Pressure (DBP), Pulse Rate

(PR), Respiratory Rate (RR), temperature, and weight (kg). A data listing of vital signs will also be provided.

5.3.4. Electrocardiogram

Frequency table for the following interpretations will be generated:

- Widespread of ST elevation normal
- PR-segment depression
- ECG Interpretation
 - Normal
 - abnormal not clinically significant, and abnormal clinically significant)
 - Abnormal not consistent with pericarditis but clinically significant
 - Abnormal consistent with pericarditis

Shift table for shifts from baseline to the last post-baseline assessment in the treatment period and extension period in the overall interpretation based on local read will be created. All ECG data will be provided as a by-subject listing.

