3. GENERAL STATISTICAL CONSIDERATIONS

3.1. General Methods

Statistical analysis will be performed using SAS® software Version 9.4 or later. Continuous variables will be summarized using the mean, the standard deviation, median, minimum value, and maximum value. Time-to-event variables will be summarized using percent censored, event rate, and 25th, 50th, and 75th percentiles with 95% CI, if estimable. Categorical variables will be summarized using frequency counts and percentages. Data will be listed in data listings.

At RI, RW, and LTE periods, baseline will be the last value before the first dose of study drug within each individual period unless otherwise specified. For change-over-time endpoints in the RW period, by-visit analysis will be performed at each scheduled visit for at least 24 weeks.

When weekly average of NRS is used, it will be calculated based on every 7 days starting on the day after the first injection in each period. If there are missing values during the 7- day period, the average will be calculated based on the non-missing values. If 50% or more values (≥ 4 days) are missing, the average value will be set to missing.

By-visit analyses will be based on nominal visits and observed data, with unscheduled visits excluded.

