analysis of the primary endpoint. The same censoring rules will apply. The variance of the difference in proportion between treatment arms will be the sum of the variance in each arm. The p-value and 95% CI will be calculated using a normal approximation.

8. Time to pericarditis pain NRS ≥ 4

Use the same method for the primary endpoint.

9. Time to CRP level ≥ 1 mg/dL. This is for elevation of CRP for causes.

Use the same method for the primary endpoint. A manual review for any CRP ≥ 1 mg/dL will be performed to make sure that the CRP increase was caused by pericarditis.

10. Time to pericardial rub

Use the same method for the primary endpoint. Subjects with pericardial rub at RW baseline will be excluded from the analysis.

11. Time to widespread ST-segment elevation or PR-segment depression on ECG

Use the same method for the primary endpoint. Subjects with either condition at RW baseline will be excluded.

12. Time to new or worsening pericardial effusion on ECHO

Use the same method for the primary endpoint. Proportion of subjects with new or worsening in pericardial effusion on ECHO and its 95% CI in each arm will be estimated using the K-M method.

13. Change in category of ECHO pericardial effusion size at week 24 and end of RW based on central labs

- The ITT Week 24 analysis set will be used for this endpoint. Effusion size in ECHO has the following categories:
- None or Trivial/Physiologic
- Small
- Moderate
- Large
- Very Large
- NM/ND (Not Measurable/Not Recorded by Site)

Shift tables for change from RW baseline to RW weeks 24 and to end of RW visit will be generated. Due to potentially different number of subjects receiving bailout rilonacept between treatment arms, there will be no hypothesis testing for this endpoint.

Endpoints 14-16 will be summarized for data before receiving bailout rilonacept and

for data including bailout riloncept in each arm. P-values will not be provided due to potentially different number of subjects receiving bailout riloncept.

14. Change over time in central-lab CRP level

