5.3. Safety Analysis

The following safety endpoints will be analyzed:

- Adverse events,
- Clinical laboratory parameters,
- Serology parameters,
- Hematology parameters,
- Non-fasting lipid panel,
- Pregnancy test,
- Vital signs,

- Urinalysis,
- Electrocardiogram, and
- Physical examination.

Descriptive statistics will be used to summarize safety endpoints for all subjects by the following periods:

- RI period (KPL-914)
- RW period
 - KPL-914 vs. Placebo Including Bailout Rilonecept
 - KPL-914 vs. Placebo before Bailout Rilonecept
- LTE period
- Study overall (RI through LTE), KPL-914 or placebo, regardless of receiving bailout Rilonecept.

Two-sided 95% CIs will be presented where meaningful. Data summaries will be displayed for clinical laboratory analyses, vital signs measurements, ECGs, and physical examination findings.

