b Scheduling of visits within visit windows requires cautious planning to ensure there is no interruption to subject evaluation and study drug treatment.

c Full physical examination includes at minimum evaluation of vital signs, head, eye, ear, nose, and throat as well as cardiovascular, dermatological, musculoskeletal, respiratory, GI, genitourinary, and neurological systems. The decision to perform examination of genitourinary system should be guided by clinical judgement.

Statistical Analysis Plan

Kiniksa Pharmaceuticals, Ltd.
Study KPL-914-C002

-
- d Abbreviated physical examination includes at minimum evaluation of vital signs, lung and heart sounds, including evaluation for pericardial rub.
 - e ECHO is required to be obtained according to the central core lab parameters and then read locally and submitted to the central core lab for separate review and analysis.
 - h Lipid panels are non-fasting and are to be drawn at a minimum of every 6months during the randomization withdrawal and LTE periods, or more frequently as needed, with mandated evaluations as detailed in the schedule of events.
 - j For women of child bearing potential - urine pregnancy testing can be repeated as needed throughout the course of the study and serum pregnancy can be drawn as needed; urine pregnancy is required to be performed at enrollment and 6 weeks after the last dose of study drug.
 - l Adverse event reporting begins following the subject providing informed consent.
 - m All procedures are to be completed prior to study drug administration.
 - o Study drug administration is once weekly with a minimum of 5 days required between doses.
 - s PK and ADA samples will be collected prior to study drug administration. PK at enrollment/baseline will be taken from ADA. As required, ADA samples will be collected at EOS, ET, and Unscheduled visits.
 - t The EORW visit serves as both the last visit of the RW period and the baseline visit of the LTE period.
 - u For all subjects, the final clinic visit of the end of RW period is to be scheduled once the End of the Randomization Withdrawal end date is announced by Sponsor. This includes subjects that are taking blinded study drug, open-label rilonacept, or who have prematurely discontinued study drug.
 - v Study drug administration to occur only after subject provides informed consent for the open-label extension period.

Table 6: Study Schedule of Activities – Long Term Extension

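### The ECG shift table in SAP 5.3.4 uses only the last post-baseline ECG, so an abnormality that resolves earlier in the RW or LTE period shows as no shift

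*SAP*

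**What the plan says.** SAP 5.3.4 plans three ECG outputs.

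- **Shift table.** "Shift table for shifts from baseline to the last post-baseline assessment in the treatment period and extension period", based on the overall interpretation from the local read.
- **Frequency table.** "Frequency table for the following interpretations will be generated". It covers ST elevation, PR depression and the interpretation categories. One of those categories is a clinically significant abnormality not consistent with pericarditis. No visits are named.
- **Listing.** "All ECG data will be provided as a by-subject listing".

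Other sections bear on how these work.

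- SAP 5.3.2 treats laboratory shifts differently: "Shift tables from baseline condition to the condition at each visit will also be provided".
- SAP 3.1 sets the general rule for by-visit summaries: "By-visit analyses will be based on nominal visits and observed data, with unscheduled visits excluded".
- SAP 5.3 lists ECG among the safety endpoints and splits the RW period into a summary including bailout and a second one, "KPL-914 vs. Placebo before Bailout Rilonecept".
- SAP 13.1, Table 5, schedules an ECG at the end-of-RW (EORW) visit. Footnote u extends that visit to all subjects: "This includes subjects that are taking blinded study drug, open-label rilonacept, or who have prematurely discontinued study drug".
- SAP 5.2.2.3, endpoint 11, is "Time to widespread ST-segment elevation or PR-segment depression on ECG", analysed by the method of the primary endpoint.

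**The concern.** A safety shift table is where a reader looks for deterioration on treatment. If only the last ECG in a period counts, a subject who is normal at baseline, abnormal mid-period and normal at the end is tabulated as normal to normal. The laboratory tables would show the same course, because they report each visit. The SAP gives no reason for the narrower ECG rule.

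The category that matters most for drug safety is the clinically significant abnormality not consistent with pericarditis. If the shift table misses it and no other summary is sure to pick it up, it can end up only in a by-subject listing, with no count by arm or period.

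**Working it through.** No arithmetic applies. The check sets the ECG schedule in SAP 13.1 (Tables 4 to 7) beside the shift rule, then asks which other outputs would show an ECG that the shift table drops.

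**Step 1. Post-baseline ECGs by period**

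| Period | Scheduled | Other possible |
|---|---|---|
| RI | Week 12 only | EOT |
| RW | Week 24, EORW | recurrence assessment, EOT |
| LTE | Week 24, 18-month assessment | recurrence assessment, EOT |

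In RI no scheduled ECG is dropped. In RW and LTE more than one ECG can occur, and all but the last are dropped. RW is event-driven, so a subject randomized less than 24 weeks before closure may have EORW as the only scheduled RW ECG and loses nothing.

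The shift sentence speaks of a treatment period without mapping it to RI or RW. If the two were pooled, three scheduled post-baseline ECGs (RI Week 12, RW Week 24, EORW) would reduce to one. Section 3.2 of the SAP addendum, which confines safety summaries to RI, RW and LTE, points to separate periods, but 5.3.4 does not say so.

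**Step 2. Effect of the bailout split in RW**

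- *Summary including bailout.* The EORW ECG is normally the last one, so it replaces an earlier recurrence-visit ECG. For a bailed-out subject it is usually taken after open-label rilonacept has started.
- *Summary before bailout.* The last ECG of a bailed-out subject would usually be the recurrence-visit ECG, which therefore enters the table.
- *Recurrence without bailout.* These subjects continue blinded drug (SAP 2.1), so the EORW ECG normally replaces the recurrence ECG in both summaries.

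**Step 3. Would another output show the dropped ECG?**

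| Output | Covers | Does not cover |
|---|---|---|
| RW endpoint 11 (5.2.2.3) | first ST or PR change, even if it resolves | other ECG abnormalities; LTE; subjects with either finding at RW baseline |
| Recurrence evidence (5.2.1.2) | pericarditis-type ECG changes, summarized and/or listed | abnormalities not consistent with pericarditis |
| LTE endpoint 13 (5.2.3.2) | pericardial signs on ECG, through LTE Week 24 | other abnormalities; later visits |
| Frequency table (5.3.4) | all interpretation categories | unknown, because no visit basis is stated |
| Listing (5.3.4) | everything | gives no counts |

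The frequency table decides the matter. If it is run by visit, section 3.1 removes unscheduled visits. Section 5.2.1.1 allows a suspected recurrence to be seen at a scheduled or an unscheduled visit, and the SAP does not say how that ECG is classed. A transient non-pericarditis abnormality found outside a nominal visit could then reach only the listing.

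**The case against.** The strongest reply is that little is really lost. The listing holds every ECG. Pericarditis-type ECG changes in RW have a time-to-event analysis that counts a first occurrence whether or not it resolves. ECG and laboratory shifts may legitimately follow different conventions. All of this stands, and it limits the point to one table and mainly one category of abnormality.

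A reader might infer that essentially every recurrence-visit ECG is lost, since RW closes only after at least 22 confirmed recurrences and EORW follows. The documents do not support that. The before-bailout summary would usually end on the recurrence ECG of a bailed-out subject. The 22 also counts recurrences, not abnormal ECGs: ECG change is one of six supportive items, and the first recurrence criterion needs only pain and CRP. Nor can a fraction of missed abnormalities be derived from the number of visits, because nothing in the SAP says when abnormalities occur.

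The last objection concerns the remedy, and it also stands. Recurrence ECGs are triggered by the efficacy outcome. With a planned hazard ratio of 0.244 (SAP 2.3.1), placebo subjects are expected to recur more often and so to have more such ECGs. A single worst-value table that includes them would ascertain the arms unequally and carry the efficacy result into a safety table. In addition, 5.3.4 gives no ranking of the interpretation categories, so worst is not yet defined.

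**Conclusion.** The point holds in a limited form. In RW and LTE, the shift to last reports an abnormality that resolves before the final ECG as no shift. A transient, clinically significant abnormality not consistent with pericarditis is covered by neither endpoint 11 nor the recurrence summary, and it may appear only in the listing.

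The size cannot be stated, because the documents give no frequency of transient ECG abnormalities. The conclusion rests on the ECG schedule in Tables 4 to 7, on the literal reading of the shift rule, and on the before-bailout RW summary being produced for ECG as section 5.3 implies. Addendum 3.2 does not say that this split is dropped.

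This is a minor safety-reporting matter. It affects neither the primary nor the major secondary analyses.

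**What to change.** In SAP 5.3.4:

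1. Keep the shift to the last post-baseline ECG, and replace the reference to a treatment period with named periods.
2. Add a shift from baseline to the worst post-baseline interpretation for RI, RW including bailout, RW before bailout, and LTE.
3. State the severity order of the interpretation categories, and whether the clinically significant non-pericarditis category ranks above, below or level with the pericarditis-consistent one.
4. Present the worst-value shift twice: on scheduled and EOT ECGs, then with recurrence-visit and unscheduled ECGs added. Give the number of ECGs per subject by arm beside both.
5. State which visits the frequency table uses, and whether recurrence-visit and unscheduled ECGs count.

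The cost is SAP wording and one additional programmed table in two versions, with no new data. The version with recurrence ECGs will have unequal ascertainment by arm and should carry a footnote saying so; the version on scheduled and EOT ECGs largely avoids this.

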5.3.5. Physical Examination

There are full and abbreviated physical examinations. Full physical examination includes at minimum evaluation of vital signs, head, eye, ear, nose, and throat as well as cardiovascular, dermatological, musculoskeletal, respiratory, gastrointestinal (GI), genitourinary, and neurological systems. The decision to perform examination of genitourinary system should be guided by clinical judgement. Abbreviated physical examination includes at minimum evaluation of vital signs, lung and heart sounds, including evaluation for pericardial rub.

Present or absent in pericardial rub will be recorded. For each assessment of body system, the result will be recorded as normal, abnormal (not clinically significant), or abnormal (clinically significant). The number and percentage of subjects in each result category will be summarized by body system and visit, as well as by arm in the RW period.

All physical examination data will be provided in a listing.

6. PHARMACOKINETIC ANALYSES

For all subjects, serum samples will be collected at time points shown in Section 13.1 in order to quantify concentrations of riloncept. Only individual listings of serum concentrations will be provided. The analysis plan for PK data will be described in a separate document.

7. PHARMACOGENOMICS SUBSTUDY

Samples for pharmacogenomics in the substudy will be collected according to the Study Schedule of Activities. More details of the analysis will be provided in a separate document.

8. ANTI-RILONACEPT ANTIBODIES

Blood sample for testing anti-rilonacept antibody (ADA) will be collected at RI baseline, RI weeks 2, 6, 12 (= RW baseline), RW week 24, end of RW/LTE baseline, and LTE week 24. ADA status will be categorized as follows.

1. Treatment-emergent ADA, including treatment induced or boosted [increased by one quartile (with all titers collected) from the previous assessment]
2. Prior existing ADA (without treatment boosted)
3. ADA negative at every assessment.

For subjects with treatment-emergent ADA, the maximum post-baseline titer level (low, medium, high) will be summarized. The 3 levels (low, medium, high) will be divided based on 25th and 75th percentiles from all ADA titers pooled.

The following endpoints will be summarized for each category of ADA status above:

- Number and percentage of subjects with injection site reactions within 24 hours of administration
- Subjects with Neutralizing antibody in the first 2 categories above.

A summary table will be provided for number and percent of subjects with positive or negative anti-rilonacept antibody by visit. Individual's ADA status and titer level (if positive) at each visit will be provided.

The number and percent of subjects with anti-rilonacept-antibody positive at any visit vs. those with negative at every visit will also be provided. The summary statistics of CRP and NRS level will be provided for these 2 subsets of subjects at each visit by study period, and by treatment arm in the RW period (before vs. after receiving bailout rilonacept and overall).

The following 3 categories will be used in the subgroup analysis for the primary endpoint, Summary of NRS scores and CRP levels over time, summary of TEAEs (overall and drug related), and blood concentration over time:

1. Subjects with ADA Positive at Any Assessment
2. Subjects with ADA Positive and Neutralizing Antibody at Any Assessment
3. Subjects with ADA Negative at Every Assessment

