3.4. Subgroups to be Analyzed

Subgroup analyses for the primary efficacy endpoint will be performed by the following variables for the RW period:

- Oral CS use at baseline (RI baseline, i.e., beginning of RI period): yes or no
- Diagnosis of recurrent idiopathic pericarditis (RI baseline): yes or no
- Age group: 12 - <18, 18 - <65, and 65 – (maximum age in ITT analysis set)
[Analysis for the pediatric group (12- <18) may not be performed if the sample size is too small.]
- Gender: males vs. females
- Race: Caucasian vs. non-Caucasian
- Region: USA vs. non-USA
- Number of pericarditis episodes at enrollment (including index and qualifying episodes): < 5 vs. ≥ 5

- ADA status: ADA positive at any assessment, ADA positive with neutralizing antibody at any assessment, and ADA negative at every assessment.

P-values and summary statistics will be generated following Section 5.2, with the understanding that the sample size is likely too small to have an adequate power. The forest plot with 95% CI will be provided for the primary efficacy endpoint.

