 - p Randomization and subsequent study drug dispensing to occur after confirmation of Clinical Response (see definition of Clinical Response in Section 6.2.2).
 - q The Randomization visit serves as both the RI Week 12 visit and the RW baseline visit.
 - s PK and ADA samples will be collected prior to study drug administration. PK at enrollment/baseline will be taken from ADA

Statistical Analysis Plan

Kiniksa Pharmaceuticals, Ltd.
Study KPL-914-C002**Table 5: Study Schedule of Activities – Randomized Withdrawal**

Trial Period	RANDOMIZED WITHDRAWAL (event-driven) ^m								END OF RANDOMIZED WITHDRAWAL (EORW) ^t
	RW Week 4	RW Week 8	RW Week 12	RW Week 16	RW Week 20	RW Week 24	RW Every 8 Weeks	RW Every 8 Weeks	
Visit Window ^b (days)	+/- 2	+/- 2	+/- 2	+/- 2	+/- 2	+/- 2	+/- 2	+/- 2	+/- 7
Visit Type	TC/RN	Clinic	TC/RN	Clinic	TC/RN	Clinic	TC/RN	Clinic	Clinic
Informed Consent Form									X
Concomitant medications	X	X	X	X	X	X	X	X	X
Pericarditis Concomitant medications	X	X	X	X	X	X	X	X	X
Full Physical Examination ^c						X			X
Abbreviated Physical Examination ^d									
Body weight and height		X		X		X		X	X
12-Lead ECG						X			X
Echo ^e						X ^e			X ^e
MRI (substudy only)						X			
Pericardial pain (11-point NRS)	DAILY								
EQ-5D						X			X
SF-36						X			X
ISI						X			X
PGIPS		X		X		X		X	X
PGA-PA		X		X		X		X	X
Hematology, Chemistry Labs (Central)		X				X		X	X
Lipid Panel (Central) ^h						X			X
CRP (Local)									

Statistical Analysis Plan

Kiniksa Pharmaceuticals, Ltd.
Study KPL-914-C002

Trial Period	RANDOMIZED WITHDRAWAL (event-driven) ^m								END OF RANDOMIZED WITHDRAWAL (EORW) ^t
Visit Name	RW Week 4	RW Week 8	RW Week 12	RW Week 16	RW Week 20	RW Week 24	RW Every 8 Weeks	RW Every 8 Weeks	Per Announced End Date ^u / LTE-Baseline
Visit Window ^b (days)	+/- 2	+/- 2	+/- 2	+/- 2	+/- 2	+/- 2	+/- 2	+/- 2	+/- 7
Visit Type	TC/RN	Clinic	TC/RN	Clinic	TC/RN	Clinic	TC/RN	Clinic	Clinic
CRP(Central)	X	X	X	X	X	X	X	X	X
PK (Central)		X				X			X
ADA (Central)						X			X
Biomarkers (Central)		X				X			
Urine Pregnancy ^j (Local or Central)									X
Urinalysis									X
IWRS Subject Status Update									X
IWRS Weight Input (pediatric only)		X		X		X		X	X
IWRS Drug Dispensing		X		X		X		X	X ^v
In Clinic Study Drug Administration ^o		X		X		X		X	X ^v
Outpatient Study Drug Administration ^o	X	WEEKLY							
Study Drug Compliance Review	X	X	X	X	X	X	X	X	X
Assessment of Pericarditis Recurrence	X	X	X	X	X	X	X	X	X
Adverse Event Reporting ^l	X	X	X	X	X	X	X	X	X

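### SAP v2.0 Section 8 judges boosted ADA against the previous sample rather than RI baseline, so a dip and recovery counts as treatment-emergent; its sampling list also disagrees with Tables 4 and 7.

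*SAP*

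**What the plan says.** Section 8 of SAP v2.0 sorts subjects into treatment-emergent ADA (induced or boosted), prior existing ADA that was not boosted, and ADA negative throughout. The boosting rule reads "boosted [increased by one quartile (with all titers collected) from the previous assessment". Injection site reactions within 24 hours of dosing are summarized for each category, and neutralizing antibody for the first two.

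On sampling, Section 8 says ADA blood is "collected at RI baseline, RI weeks 2, 6, 12 (= RW baseline), RW week 24", and then at EORW/LTE baseline and LTE Week 24. It also promises a by-visit table: "A summary table will be provided for number and percent of subjects with positive or negative anti-rilonacept antibody by visit".

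The schedules in Section 13.1 give a different list:

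- Table 4 marks ADA at RI Baseline, RI Week 2 and RI Week 6. The RI Week 12/RW Baseline cell is empty.
- Table 5 begins at RW Week 4 and marks ADA at RW Week 24 and EORW. Its footnote s adds: "As required, ADA samples will be collected at EOS, ET, and Unscheduled visits".
- Table 7 marks ADA at the recurrence assessment, EOT and SFU visits. Section 8 lists none of these.

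The ADA subgroups for the primary endpoint, in Section 3.4, are defined differently: "ADA status: ADA positive at any assessment, ADA positive with neutralizing antibody at any assessment, and ADA negative at every assessment".

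**The concern.** The category for prior existing ADA is anchored before drug exposure, so its counterpart, boosting, should be measured from the same point. Measured from the previous sample, a titer that only recovers lost ground looks like a response to drug. The subject then moves from the prior-existing to the treatment-emergent category, and any injection site reaction or neutralizing result moves too.

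The sampling mismatch raises a second question: does an ADA status at randomization exist? If Table 4 is right, it does not. ADA that arose in the last half of the run-in would then first appear at a visit in the RW period, when half the subjects are assigned to placebo, and the by-visit table would have no scheduled data at RW baseline.

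**Working it through.** **Boosting rule**

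Assumption: an increase of one quartile means moving up at least one of four titer categories. The subject is ADA-positive at RI baseline and has a titer at every sample.

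1. Example: category 3 at RI baseline, 2 at Week 2, 3 at Week 6. The steps are −1 and +1, so Section 8 calls this boosted. The highest later category minus baseline is 3 − 3 = 0, so nothing rose above the pre-drug level.
2. Take the four samples RI baseline, Week 2, Week 6 and RW Week 24. There are 4⁴ = 256 possible sequences.
3. Sequences never above the baseline category b number b³ for each b: 1 + 8 + 27 + 64 = 100.
4. Of these, the ones with no upward step are the non-increasing sequences: C(7,4) = 35.
5. Flagged as boosted but never above baseline: 100 − 35 = 65 of 256.
6. With a Week 12 sample there are five samples and 4⁵ = 1,024 sequences. Never above baseline: 1 + 16 + 81 + 256 = 354. Non-increasing: C(8,5) = 56. Difference: 298 of 1,024.
7. Opposite error: a sequence that does exceed its baseline category must contain an upward step, so the previous-sample rule always flags it. The count is 0 in both cases.
8. With RI baseline as comparator the discordant counts fall to 0 by definition.

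The SAP gives no titers, so these are counts of possible patterns and say nothing about how many subjects would be affected. The text also permits another reading, in which one quartile is a fixed titer increment. Under that reading a gradual rise made of small steps could be missed.

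**Sampling list**

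1. The Table 4 ADA row has ten cells, with marks in the RI Baseline, Week 2 and Week 6 columns. The hematology/chemistry, lipid and PGIPS rows also have ten cells and do carry a mark at Week 12, so the columns are aligned.
2. The copy of Table 4 in SAP v1.0 shows the same ADA row against the same Section 8 text. The list of changes from v1.0 to v2.0 does not mention it.
3. No other table can hold the sample. Table 4 states: "The Randomization visit serves as both the RI Week 12 visit and the RW baseline visit".
4. If Table 4 is right, RI Week 6 to RW Week 24 is 6 + 24 = 30 weeks between routine samples, covering the last 6 of 12 run-in weeks. If Section 8 is right, that interval splits into 6 and 24 weeks.

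**The case against.** Several objections are sound and limit the point.

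- **A reader might infer that run-in immunogenicity is missed.** It is not. RI baseline, Week 2 and Week 6 are sampled on either reading, and later positivity can still be detected. Only its timing, the status at randomization and transient positivity are at stake.
- **A reader might take 30 weeks as the general gap.** Table 7 samples at recurrence, EOT and SFU. Under the planning assumptions of Section 2.3.1 (exponential, placebo median 8 weeks), 1 − 0.5^(24/8) = 87.5% of placebo subjects would recur by RW Week 24, with an ADA sample at the recurrence visit. The median interval from RI Week 6 would then be 6 + 8 = 14 weeks.
- **A reader might take Table 4 as the true schedule.** Sites work from the protocol, which is not shown. Section 8 may be right and Table 4 short of one mark. Machine reading adds doubt: the two copies of Table 4 differ in the last column of the pain row. The documents do not say which passage is correct.
- **Adding a blood draw is not a remedy.** Section 11.2 says the RW period was nearing its end when the pandemic began, and the list of changes says every subject had enrolled 12 weeks before the cutoff.
- **The boosting rule has limited reach.** It is prespecified, uses pooled rather than arm-specific titers, applies only to subjects with pre-existing ADA, and feeds descriptive tables. All of that stands, but none of it makes recovery to a pre-drug level a treatment-emergent response.

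**Conclusion.** Two things hold. First, the boosting rule is wrong as written: it classes a fall followed by a return to the RI-baseline titer as treatment-emergent. Under the category reading the error runs only that way (65 of 256 patterns with four samples, 298 of 1,024 with five). The number of subjects affected cannot be estimated from the SAP. The misclassification carries into the injection site reaction and neutralizing-antibody summaries by ADA category.

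Second, Section 8 and Table 4, as read, disagree on the RI Week 12 sample, and Section 8 leaves out the Table 7 samples. This is a matter of reconciling the passages. It becomes a limitation of the immunogenicity summaries only if the Week 12 sample was not taken.

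A reader might infer that the ADA subgroups of the primary endpoint inherit the boosting error. They do not: they rest on ever or never positive and on neutralizing status. The primary and major secondary tests use no ADA category. The effect is confined to descriptive immunogenicity reporting.

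**What to change.** 1. In Section 8, define boosted ADA as a rise above the subject's RI-baseline titer by a stated amount, fixed before unblinding and not derived from quartiles of the pooled titers. This costs one sentence.
2. Establish whether the RI Week 12/RW baseline sample was collected. If it was, add the mark to Table 4. If it was not, remove that time point from Section 8 and from the by-visit table, and state that ADA arising between RI Week 6 and randomization cannot be separated from ADA first detected in RW.
3. Add the recurrence, EOT and SFU samples of Table 7 to the Section 8 list.

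These are edits to text and tables, with a small change to the derivation of the ADA categories. No visit or sample is added and no planned test changes.
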